5.2 Secondary Endpoints

5.2.1 Uncorrected Visual Acuity

The primary analysis will be repeated for LogMAR of UCVA separately for each eye (primary eye and fellow eye).

5.2.2 Maximum Corneal Curvature

The primary analysis will be repeated for K_{\max} separately for each eye (primary eye and fellow eye). Additionally, the change from baseline will be categorized defined by: $\leq -2D$, -1.99 - $1.5D$, $-1.49D$ to $1D$, $.99D$ to $.5D$, $-.49D$ to $0D$, $.01D$ to $.49D$, $0.5D$ to $.99D$, $1D$ to $1.49D$, $1.5D$ to $1.99D$, $\geq 2D$. Frequency of patients in each category for each eye will be presented at Months 3, 6, and 12.

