3.8.2 Definition of Study Baseline

Study baseline is defined as the last observation obtained on or prior to the start of the procedure on the first eye on Study Day 1.

Change from baseline is defined as post-baseline assessment minus baseline assessment. Baseline value will not be carried forward to impute the post-baseline values.

For efficacy measures performed on individual eyes, baseline will be determined for each eye separately based on the date of the procedure on each particular eye.

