8.2 Appendix B: Tables, Listings, and Figures

Table 1	Disposition	Treated Analysis Set
Table 2.1	Demographics	Treated Analysis Set
Table 2.2	Demographics	Efficacy Analysis Set
Table 3	CXL Procedures	Safety Analysis Set
Table 4.1.1	Summary of Corrected Distance Visual Acuity	Efficacy Analysis Set
Figure 4.1.1	Mean +/- SE of Changes in Corrected Distance Visual Acuity	Efficacy Analysis Set
Table 4.1.2	Analysis of Changes in Corrected Distance Visual Acuity	Efficacy Analysis Set
Table 4.2.1	Summary of Corrected Distance Visual Acuity in Patients < 22 Years Old	Efficacy Analysis Set
Figure 4.2.1	Mean +/- SE of Changes in Corrected Distance Visual Acuity in Patients < 22 Years Old	Efficacy Analysis Set
Table 4.2.2	Analysis of Changes in Corrected Distance Visual Acuity in Patients < 22 Years Old	Efficacy Analysis Set
Table 4.3.1	Summary of Corrected Distance Visual Acuity in Patients with Baseline Kmax ≥ 47	Efficacy Analysis Set
Figure 4.3.1	Mean +/- SE of Changes in Corrected Distance Visual Acuity in Patients with Baseline Kmax ≥ 47	Efficacy Analysis Set
Table 4.3.2	Analysis of Changes in Corrected Distance Visual Acuity in Patients with Baseline Kmax ≥ 47	Efficacy Analysis Set
Table 5.1.1	Summary of Uncorrected Visual Acuity	Efficacy Analysis Set
Figure 5.1.1	Mean +/- SE of Changes in Uncorrected Visual Acuity	Efficacy Analysis Set
Table 5.1.2	Analysis of Changes in Uncorrected Visual Acuity	Efficacy Analysis Set
Table 5.2.1	Summary of Uncorrected Visual Acuity in Patients < 22 Years Old	Efficacy Analysis Set
Figure 5.2.1	Mean +/- SE of Changes in Uncorrected Visual Acuity in Patients < 22 Years Old	Efficacy Analysis Set
Table 5.2.2	Analysis of Changes in Uncorrected Visual Acuity in Patients < 22 Years Old	Efficacy Analysis Set
Table 5.3.1	Summary of Uncorrected Visual Acuity in Patients with Baseline Kmax ≥ 47	Efficacy Analysis Set
Figure 5.3.1	Mean +/- SE of Changes in Uncorrected Visual Acuity in Patients with Baseline Kmax ≥ 47	Efficacy Analysis Set
Table 5.3.2	Analysis of Changes in Uncorrected Visual Acuity in Patients with Baseline Kmax ≥ 47	Efficacy Analysis Set

Table 6.1.1	Summary of Maximum Corneal Curvature	Efficacy Analysis Set
Figure 6.1.1	Mean +/- SE of Maximum Corneal Curvature	Efficacy Analysis Set
Table 6.1.2	Analysis of Changes in Maximum Corneal Curvature	Efficacy Analysis Set
Table 6.1.3	Categorical Shifts in Maximum Corneal Curvature	Efficacy Analysis Set

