Table 6.2.1	Summary of Maximum Corneal Curvature in Patients < 22 Years Old	Efficacy Analysis Set
Figure 6.2.1	Mean +/- SE of Maximum Corneal Curvature in Patients < 22 Years Old	Efficacy Analysis Set
Table 6.2.2	Analysis of Changes in Maximum Corneal Curvature in Patients < 22 Years Old	Efficacy Analysis Set
Table 6.2.3	Categorical Shifts in Maximum Corneal Curvature in Patients < 22 Years Old	Efficacy Analysis Set
Table 6.3.1	Summary of Maximum Corneal Curvature in Patients with Baseline Kmax ≥ 47	Efficacy Analysis Set
Figure 6.3.1	Mean +/- SE of Maximum Corneal Curvature in Patients with Baseline Kmax ≥ 47	Efficacy Analysis Set
Table 6.3.2	Analysis of Changes in Maximum Corneal Curvature in Patients with Baseline Kmax ≥ 47	Efficacy Analysis Set
Table 6.3.3	Categorical Shifts in Maximum Corneal Curvature in Patients with Baseline Kmax ≥ 47	Efficacy Analysis Set
Table 7.1	Overview of Adverse Events	Safety Analysis Set
Table 7.2	Treatment Emergent Adverse Events by SOC and PT	Safety Analysis Set
Table 7.3	Treatment Emergent Anticipated Adverse Events by SOC and PT	Safety Analysis Set
Listing 1	Subject Disposition	Treated Analysis Set
Listing 2	Listing of Patients with Re-Treatment with CXL	Treated Analysis Set
Listing 3	Listing of Aes	Safety Analysis Set

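### Three Kmax change bands in SAP 5.2.2 are printed without a minus sign, so the categories overlap, one interval appears twice and another has no band of its own (a minor correction to three descriptive tables)

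*SAP*

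**What the plan says.** SAP 5.2.2 repeats the primary analysis for Kmax and adds a classification of the change into ten bands. The first is a fall of 2 D or more and the last a rise of 2 D or more. The second and third bands read "1.99 - $1.5D$, $-1.49D$ to $1D" (a minus sign precedes the first figure in the SAP). The third to fifth read "1.49D$ to $1D$, $.99D$ to $.5D$, $-.49D$ to $0D" (again with a minus sign just before the quoted run). The sixth to ninth, on the positive side, are "01D$ to $.49D$, $0.5D$ to $.99D$, $1D$ to $1.49D$, $1.5D$ to $1.99D" (a decimal point precedes the first figure).

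On use, the section says: "Frequency of patients in each category for each eye will be presented at Months 3, 6, and 12". Appendix B lists three tables built on the bands. Table 6.1.3 covers the whole efficacy analysis set ("Categorical Shifts in Maximum Corneal Curvature"), Table 6.2.3 covers younger patients ("Categorical Shifts in Maximum Corneal Curvature in Patients < 22 Years Old"), and Table 6.3.3 covers patients with baseline Kmax of at least 47.

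The direction of change is fixed in SAP 3.8.2: "Change from baseline is defined as post-baseline assessment minus baseline assessment". A negative value is therefore a fall in Kmax. Protocol 6.3 describes disease progression as an increase in Kmax, so a positive value is a change for the worse. No other section of either document restates or corrects the bands.

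**The concern.** A frequency table needs categories that do not overlap and that together cover every value. The printed list fails on the first count under any reading that leaves the third or fourth band as it stands. Three things go wrong.

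- The third band crosses zero, so it mixes eyes that improved with eyes that worsened, and it contains the fifth, sixth and seventh bands whole.
- The fourth band has the same limits as the seventh, in reverse order. One worsening interval thus has two rows.
- The mirror interval on the improvement side, -0.99 to -0.50 D, has no row of its own.

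A programmer who coded the limits as printed would count eyes in several rows, or would put them in whichever row came first. The outputs at risk are the three categorical tables. The SAP introduction says that the analyses in this version are meant to support a meeting with FDA on the Phase 3 design, so the tables have a reader outside the sponsor.

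**Working it through.** The SAP gives no figure to reproduce here. The check is whether each possible change falls in exactly one band.

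**Inputs.** The ten bands come from SAP 5.2.2 and the sign convention from SAP 3.8.2. The grid runs from -3.00 to +3.00 D in steps of 0.01 D, the precision of the printed limits. That gives 300 + 300 + 1 = 601 values.

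**Rule.** For each value v, count the bands with lower limit ≤ v ≤ upper limit. A valid list gives a count of 1 for every v.

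**Readings.** The hyphen in the second band can mean 'to' or 'minus', so both were tried. The fourth band was taken as the range 0.50 to 0.99 and, as a variant, as empty because its first limit exceeds its second.

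| Reading | In one band | In two or more | In none |
|---|---|---|---|
| A. Literal, band 2 as -1.99 to +1.50 | 301 | 300 | 0 |
| A2. As A, band 4 empty | 301 | 300 | 0 |
| B. Band 2 as -1.99 to -1.50, rest literal | 451 | 150 | 0 |
| B2. Bands 2 and 3 negative, band 4 literal | 501 | 50 | 50 |
| C. Signs restored in bands 2, 3 and 4 | 601 | 0 | 0 |

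**Where the overlaps lie.**

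- Reading A: -1.49 to -0.50 and 1.01 to 1.50 meet two bands (100 + 50 = 150 values). -0.49 to 0.49 and the value 1.00 meet three (99 + 1 = 100). 0.50 to 0.99 meets four (50). The total is 150 + 100 + 50 = 300.
- Reading B: -0.49 to 0.49 and 1.00 meet two bands (100). 0.50 to 0.99 meets three (50). The total is 150.
- Reading B2: 0.50 to 0.99 meets two bands (50). -0.99 to -0.50 meets none (50).

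**Single values.** Under A, +0.7 D falls in bands 2, 3, 4 and 7 (bands 2, 3 and 7 if band 4 is empty), 0.0 D in bands 2, 3 and 5, and -0.7 D in bands 2 and 3 only. Under B2, +0.7 D falls in bands 4 and 7, and -0.7 D in none. Under C, +0.7 D falls in band 7, 0.0 D in band 5 and -0.7 D in band 4, each once.

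Values from -0.99 to -0.50 D are left unclassified only under B2. In the literal readings the over-wide bands absorb them. What holds for A to B2 alike is that this interval has no dedicated band.

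**Rounding.** Reading C is complete only at 0.01 D. A change held to more decimals could fall between printed limits, for example between -2 and -1.99. SAP Appendix D covers the display of results and the rounding of percentages, and does not say how change is rounded before it is classified.

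**The case against.** The strongest reply is that this is a typographical slip with an obvious cure. The list runs in order from -2 to +2 D, the positive side is intact, and restoring three signs gives a clean partition. The signs may even have been lost when the PDF was converted to text: the second band is set differently from the others, and its hyphen may itself be a minus sign. Minus signs do survive at the start of four bands (the limits -2, -1.99, -1.49 and -0.49), so such a loss would have been selective, but it cannot be ruled out from the text alone. The reply also notes that the tables are an additional display for a secondary endpoint, and that SAP 3.2.3.1 says no hypotheses are tested. All of this stands, and it sets the severity. It does not make the printed rule usable.

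A reader might infer two stronger points, and the documents support neither.

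- That a stated large share of eyes would be misclassified. Any percentage needs a distribution of Kmax change, and the documents give neither a mean nor a standard deviation. It also needs a programmer who assigns each eye to the first matching band of an evidently faulty list, which nothing in the SAP implies.
- That the list leans towards benefit because exactly zero sits in the band from -0.49 to 0 while its mirror starts at 0.01. The SAP labels no band as flattened or improved and defines no summed share. The row shows openly that it includes zero. The share of eyes at exactly zero depends on a recording precision that the documents do not state: a grid ten times finer makes it about ten times smaller.

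**Conclusion.** The rule is wrong as printed, and the error is minor. Three negative-side bands lack a minus sign. On the literal reading 300 of 601 grid values fall in more than one band, and each partial repair tried still leaves overlaps. With all three signs restored, all 601 values fall in exactly one band. These are counts of possible values, not of eyes.

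The effect is confined to the descriptive Tables 6.1.3, 6.2.3 and 6.3.3. The mean changes, confidence intervals and pairwise differences for Kmax (Tables 6.1.2, 6.2.2 and 6.3.2) do not use the bands and are unaffected, as are the primary endpoint and the safety outputs.

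The conclusion rests on two assumptions: that the source PDF shows the same text, and that change is classified at the 0.01 D precision of the printed limits. If the signs are present in the source, only the rounding rule remains to be added.

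**What to change.** Check SAP 5.2.2 in the source PDF. If the signs are absent there, replace the list with these ten bands, in dioptres:

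- ≤ -2.00
- -1.99 to -1.50
- -1.49 to -1.00
- -0.99 to -0.50
- -0.49 to 0
- 0.01 to 0.49
- 0.50 to 0.99
- 1.00 to 1.49
- 1.50 to 1.99
- ≥ 2.00

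State that change is rounded to 0.01 D before classification, and use this one list for Tables 6.1.3, 6.2.3 and 6.3.3. A separate row for no change is optional.

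The cost is a sentence or two in the SAP and one category definition in the program. No data, sample size or other analysis changes.

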6. SAFETY

Safety data will be summarized using the safety population. Missing data will not be imputed for safety analyses. In the presence of partial dates, the available data (month and/or year) will be compared to the appropriate study reference dates to identify the most likely treatment received.

6.1 Treatment Emergent Adverse Events

6.1.1 General Considerations for Analysis of Adverse Events

General considerations for AE summaries and calculations are:

- Multiple events by preferred term (PT) and system organ class (SOC) will be counted once only per subject.

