4.0 STUDY TREATMENTS

4.1 INVESTIGATIONAL TREATMENT

One or both eligible eyes may be enrolled and procedure performed on the same day or on different days. Subjects eligible for enrollment will be instructed to instill Polytrim (or Floraquinolone or other appropriate broad spectrum antibiotic if the subject is hypersensitive) 4 times daily into the eligible eye(s) one day prior to treatment

- A. Instill anesthetic eye drops.
- B. Place a lid speculum in each eye undergoing treatment.
- C. Use a sterile ophthalmic sponge hydrated with saline or anesthetic drops to gently swab the surface of the cornea to remove mucus and any other debris and to enhance riboflavin penetration into the cornea. The epithelium is not to be removed, as treatment with an intact epithelium has the potential to halt progression of the disease while reducing post-procedure pain, complications related to epithelial debridement, and promoting faster vision recovery to baseline CDVA.
- D. Apply a sterile corneal sponge protector to the surface of the cornea to serve as a reservoir for CXLO Corneal Strengthening Solution.
- E. Saturate the sponge protector with several drops of CXLO Corneal Strengthening Solution. Thereafter, to assure for continuous application of CXLO solution to the surface of the cornea, keep the sponge moistened by applying 1-2 drops of CXLO solution every 1-3 minutes for 10-90 minutes (this range is required as different corneas load at different rates and the surgeon will visually confirm sufficient stromal loading later in the procedure).
- F. After 10-20 minutes of saturation, remove the lid speculum. Examine the eye using a slit lamp or slit light to confirm adequate saturation of the cornea, referencing the “flip-chart” of slit-lamp images, a copy of which is provided in Appendix 1. If the cornea is not adequately saturated, repeat the CXLO Corneal Strengthening Solution application instructions above,

and re-assess corneal saturation via slit-lamp or slit light examination every 5-10 minutes until adequate corneal stromal saturation is confirmed.

- G. After confirming adequate stromal saturation, irrigate the corneal epithelium with artificial tears for approximately 30 seconds prior to UVA illumination to avoid the “sunscreen” effect of riboflavin in the epithelium.
- H. Place the lid speculum(s) prior to UVA light application.

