6.2 ADVERSE EVENT ASSESSMENT AND DOCUMENTATION

All subjects who have been exposed to the study treatment will be evaluated for adverse events. All adverse events, regardless of severity and whether or not they are ascribed to the study treatment, will be recorded in the source documents and CRF using standard medical terminology.

All adverse events will be evaluated beginning with onset, and evaluation will continue until resolution is noted, or until the investigator determines that the subject's condition is stable. The investigator will take appropriate and necessary therapeutic measures required for resolution of the adverse event. Any medication necessary for the treatment of an adverse event must be recorded on the concomitant medication case report form.

All AEs will be characterized by the following criteria:

- Date of onset
- Event diagnosis
- Intensity or severity
- Expectedness
- Relatedness to study treatment
- Treatment or action taken.
- Outcome

Whenever possible, recognized medical terms should be used when recording AEs. Colloquialisms and/or abbreviations should not be used. Only one medical concept, preferably a diagnosis instead of individual symptoms, should be recorded as the event.

If more than one distinct adverse event occurs, each event should be recorded separately. However, if known at the time of reporting, a diagnosis (i.e., disease or syndrome) should be recorded on the CRF rather than individual signs and symptoms. However, if a constellation of signs and/or symptoms cannot be medically characterized as a single diagnosis or syndrome at the time of reporting, each individual event should be recorded as a separate AE. A diagnosis that is subsequently established should be reported as follow-up information. However, signs and symptoms that are considered unrelated to an encountered syndrome or disease should be recorded as individual AEs.

Adverse events occurring secondary to other events (e.g., sequelae) should be identified by the primary cause; a "primary" event, if clearly identifiable, should represent the most accurate clinical term to record as the AE event term. For example:

Orthostatic hypotension ⇒fainting and fall to floor ⇒head trauma ⇒neck pain

The primary event is orthostatic hypotension and the sequelae are head trauma and neck pain.

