8.3 SAFETY

AEs, SAEs, and other findings will be summarized by presenting the percentages of subjects with each event. Continuous endpoints will be summarized using summary statistics such as means, medians, standard deviations, minima, maxima, and relevant percentiles.

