1.3.3 Safety Endpoints

The safety endpoints for this analysis include frequency, intensity, and relationship to study drug of adverse events and serious adverse events.

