1.4 Determination of Sample Size

Three thousand subjects will be enrolled in this open-label, prospective multicenter trial. One or both eyes of each patient may be enrolled and evaluated, based on whether treatment is unilateral or bilateral, based on clinical indications. All eyes treated (single or both eyes of an individual subject) will be included in the analysis of safety and efficacy. Additional details regarding the sample size for the study can be found in the protocol.

The sample size for this ad hoc analysis is partially driven by the enrollment date. All patients with at least one procedure performed are included in the safety analysis. Only patients with a diagnosis of keratoconus, who do not have prior conductive keratoplasty treatment, who are in the study long enough to be eligible for a Month 12 visit are considered for inclusion in the efficacy analysis. Additional details regarding the subset of patients for efficacy analysis can be found in Section 3.2.2

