2.3 Unique Patient Identification

Patient number from the CRF does not uniquely identify individual patients. If a patient initially had bilateral treatment, then all data are captured under a single patient number. If a patient initially had unilateral treatment but subsequently had the procedure performed on the untreated eye, data for the newly treated eye were captured under a different patient number. If a patient completed the month 6 assessment and the investigator elected to perform the CXL procedure again, then all data for this repeated procedure are captured under a second patient number.

Sites will provide a list of paired patient numbers that can be used to map all data for each patient to be summarized appropriately.

Patients receiving subsequent CXL therapy were re-randomized. Therefore the subsequent treatment may differ from the initial randomized treatment given during the first procedure. Efficacy summarization will be by individual eye which can accommodate the differing treatments. Adjustments to the safety analysis will need to be considered since that is done overall rather than by individual eye.

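### Adverse events are counted once per subject and, after a second procedure, assigned to the most recent treatment; with one or two eyes treated, the tables give no per-eye risk by UVA group

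*SAP*

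**What the plan says.** The number of treated eyes varies between subjects. Protocol 4.1 states: "One or both eligible eyes may be enrolled and procedure performed on the same day or on different days". SAP 1.4, like Protocol 8.0, promises that "All eyes treated (single or both eyes of an individual subject) will be included in the analysis of safety and efficacy".

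The counting rule in SAP 6.1.1 is by subject: "Multiple events by preferred term (PT) and system organ class (SOC) will be counted once only per subject". This agrees with Protocol 8.3, where adverse events are to be "summarized by presenting the percentages of subjects with each event". Tables 7.1 to 7.3 in SAP Appendix B all run on the Safety Analysis Set, which is a set of subjects. Listing 3 lists the events.

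On treatment group, SAP 2.3 states: "Patients receiving subsequent CXL therapy were re-randomized". It adds: "Adjustments to the safety analysis will need to be considered since that is done overall rather than by individual eye". Three subject-level rules appear elsewhere:

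- SAP 3.2.2 lets a subject appear in the safety set under more than one group.
- SAP 6 uses partial dates to decide which treatment most likely applied.
- SAP 6.1.3 assigns treatment-emergent events in multiply treated patients to the most recent treatment, without reference to the eye.

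Efficacy is handled eye by eye, with baseline and follow-up time tied to that eye's own procedure (SAP 2.3, 3.8.2 and 5).

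Protocol 6.2 introduces its list with "All AEs will be characterized by the following criteria". The seven items are onset, diagnosis, intensity, expectedness, relatedness, action and outcome. The affected eye is not among them.

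**The concern.** Most of the anticipated events in Protocol 6.3 (haze, epithelial defect, infiltrates, keratitis, raised pressure) happen to an eye. The trial compares UVA settings delivered to eyes, and SAP 1 says this analysis will support the design of a Phase 3 trial. The natural safety quantity is the proportion of treated eyes with an event, by the setting that eye received. No planned table gives it.

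Two separate mechanisms are at work. The counting rule makes a subject's chance of appearing in the table depend on how many eyes were treated, and collapses the second of two same-term events. The attribution rule can move a first-eye event into the second eye's group when the later procedure was randomised to a different setting. The first affects any bilaterally treated subject. The second affects only subjects with a later, re-randomised procedure.

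**Working it through.** The documents give no adverse event rate, bilateral share, between-eye correlation or safety precision target, so there is no stated figure to reproduce. What follows is an illustration.

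**Assumed inputs.** Per-eye risk of a given preferred term p = 5% or 10%; between-eye correlation r = 0.3 or 0.6; share of subjects treated bilaterally b = 30% or 60%.

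**Formulas**

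- Both eyes affected in a bilateral subject: B = p² + r·p(1−p).
- Subject percentage: S = (1−b)p + b(2p − B) = p(1+b) − bB.
- Affected eyes per subject: p(1+b).
- Share of affected eyes not counted: bB / [p(1+b)].

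Worked case, p = 0.10, r = 0.6, b = 0.6: B = 0.01 + 0.6 × 0.09 = 0.064. S = 0.16 − 0.0384 = 0.1216, which is 1.22 times p. Uncounted share = 0.0384 / 0.16 = 24.0%.

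| p | r | b | B | Subject % | Ratio to p | Uncounted |
|---|---|---|---|---|---|---|
| 5% | 0.3 | 30% | 0.01675 | 6.00 | 1.20 | 7.7% |
| 5% | 0.3 | 60% | 0.01675 | 7.00 | 1.40 | 12.6% |
| 5% | 0.6 | 30% | 0.0310 | 5.57 | 1.11 | 14.3% |
| 5% | 0.6 | 60% | 0.0310 | 6.14 | 1.23 | 23.3% |
| 10% | 0.3 | 30% | 0.0370 | 11.89 | 1.19 | 8.5% |
| 10% | 0.3 | 60% | 0.0370 | 13.78 | 1.38 | 13.9% |
| 10% | 0.6 | 30% | 0.0640 | 11.08 | 1.11 | 14.8% |
| 10% | 0.6 | 60% | 0.0640 | 12.16 | 1.22 | 24.0% |

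**Sensitivity.** The uncounted share depends mainly on correlation and bilateral share. At p = 10%, r = 0, b = 50% it is 0.5 × 0.01 / 0.15 = 3.3%. At p = 1%, r = 0, b = 50% it is 0.5 × 0.0001 / 0.015 = 0.3%. Rarity alone does not remove the effect: at p = 1%, r = 0.3, b = 50%, B = 0.0001 + 0.3 × 0.0099 = 0.00307 and the share is 0.5 × 0.00307 / 0.015 = 10.2%.

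**Same risk, different mix.** With p = 10% and r = 0.3 in two groups, 40% bilateral gives 0.14 − 0.4 × 0.037 = 12.5%, and 60% bilateral gives 0.16 − 0.6 × 0.037 = 13.8%. The difference comes only from the number of eyes treated.

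**Attribution.** Take a subject whose first eye is treated in Group 1 and whose second eye is later randomised to Group 2. Haze then appears in the first eye. SAP 6.1.3 assigns it to Group 2, while SAP 3.2.2 keeps the subject in the safety set under both groups. The event counts in Group 2's numerator and not in Group 1's, although the affected eye received the Group 1 setting. If re-randomisation is in equal proportions (the ratio is not stated), 1 − 1/3 = 2/3 of later procedures fall in a different group from the first. How many subjects have a later procedure is not given.

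**The case against.** Subject-level incidence is a legitimate summary and the one the protocol specifies. Events from either eye feed into it, so the promise to include all treated eyes is not strictly broken. This stands, and the subject tables should stay.

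A reader might infer that second-eye events vanish. They do not. A second-eye event is counted when the first eye had none. It is counted at preferred-term level when its term differs, and collapses then only in the system organ class count. The individual events remain in Listing 3. Where the second eye was treated later, its own subsequent events go to its own group.

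A reader might also infer that the UVA comparison is shown to be biased. It is not. Groups are assigned by subject, so the bilateral share at initial treatment should be similar on average, and SAP 4.3 tabulates one-eye and two-eye treatment by group. Eyes treated together appear to share one setting (Protocol 4.1), so cross-group error is confined to sequential procedures.

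Nor is it fair to say that SAP 2.3 is left with nothing behind it: sections 3.2.2, 6 and 6.1.3 supply subject-level rules. SAP 2.3 also says that a newly treated eye was captured under its own patient number, which gives a partial link to the procedure. None of these rules uses the affected eye, so the attribution problem remains.

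Two further inferences fail. The absence of an adverse event row in the visit schedule does not mean that events are not sought: Protocol 6.0 sets a reporting period and 6.2 requires evaluation of every exposed subject. And SAP 1.3.3 names "frequency, intensity, and relationship to study drug of adverse events and serious adverse events" as endpoints without requiring a table by organ class and term for each; the layout of overview Table 7.1 is not shown.

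**Conclusion.** The point holds as a missing eye-level analysis together with an attribution rule that ignores the eye. Under the assumed ranges in the table, about 8–24% of affected eyes go uncounted and the subject percentage is 1.11–1.40 times the per-eye risk. With uncorrelated eyes the uncounted share falls to about 3% or less at 50% bilateral treatment and a risk of 10% or lower. Every input is an assumption, so these figures show scale and are not estimates for this trial.

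The misattribution follows from the wording of SAP 6.1.3 and needs no assumed rate to exist. Its extent depends on how many subjects had a later procedure in a different group and then an event in the first eye. I read the rule as the last treatment before onset. Read as the last treatment overall, it would also move first-eye events that preceded the second procedure. Whether the CRF records the eye cannot be determined from the protocol or SAP. The change is worth making because it alters the safety figures carried into Phase 3 planning at low cost.

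**What to change.** 1. Keep Tables 7.1 to 7.3 by subject, as Protocol 8.3 requires.
2. Add an ocular adverse event table: eyes with the event over eyes treated, by the UVA group that eye received, with confidence intervals that allow for clustering of eyes within subject.
3. Amend SAP 6.1.3 so that an ocular event is assigned to the treatment of the affected eye. Use the most-recent-treatment rule only for non-ocular events or where the eye is unknown.
4. Put that rule in SAP 2.3 in place of the statement that adjustments need consideration.
5. Add the affected eye (right, left, both or non-ocular) to the attributes in Protocol 6.2. For past events where the CRF lacks it, recover it from the separate patient numbers and source records.

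The cost is a few extra tables, one field on the adverse event page, and some queries on past ocular events. Efficacy analyses are unaffected.
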